1.0 TRIAL SUMMARY

1.1 Objectives

1.1.1 Primary objective:

1.) To assess physician-reported acute grade 3 or greater gastrointestinal, genitourinary and hematologic toxicities at 12 weeks post-treatment for patients treated with linear energy transfer (LET)-optimized, intensity-modulated proton therapy (IMPT) and compare to contemporary controls treated with VMAT to determine the feasibility of this outcome for a future randomized trial.

1.1.2 Secondary objectives:

1.) To assess the feasibility of enrolling patients on a prospective trial delivering LET-optimized IMPT for newly diagnosed, non-metastatic anal cancer.
2.) To develop guidelines and workflow to create and deliver anal canal cancer treatments using LET-optimized IMPT.
3.) To evaluate complete response rate at 12 weeks and 24 weeks post-treatment.
4.) To evaluate local progression free survival, distant metastasis-free survival and overall survival at 24 and 48 months.
5.) To evaluate rates of patient-reported acute toxicity, function, distress and QOL at 12 weeks.
6.) To evaluate rates of patient-reported late toxicity, function, distress and QOL every 6 months for 24 months.
7.) To evaluate the value of proton therapy by comparing Time-Driven Activity-Based Costing data from the date of consultation until the date of the 12-week follow up visit post-treatment with contemporary controls treated with VMAT.

1.1.3 Exploratory objectives:

1.) To compare dose to the pelvic bone marrow, bowel, bladder and genitalia between LET-optimized IMPT, traditionally-optimized IMPT and VMAT.
2.) To assess rates of leukopenia, neutropenia and lymphopenia at 12-weeks post-treatment for patients treated with LET-optimized IMPT and compare to contemporary controls treated with VMAT.
3.) To correlate white blood cell counts (WBC), absolute neutrophil counts (ANC) and absolute lymphocyte counts (ALC) with dose to the pelvic bone marrow for patients treated with LET-optimized IMPT.

Abbreviated Title	IMPT for Anal Cancer
Trial Phase	Feasibility
Clinical Indication	Newly diagnosed, non-metastatic squamous cell carcinoma of the anal canal dispositioned to definitive chemoradiation treatment
Trial Type	Treatment
Type of control	None
Route of administration	External beam proton radiation therapy with concurrent chemotherapy
Trial Blinding	NA
Treatment Groups	Single arm, non-randomized
Number of trial subjects	40
Estimated duration of trial	9 years
Duration of Participation	9 years

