7.1 Data Collection, Management and Statistical Summary

Study data will be collected and managed using REDCap (Research Electronic Data Capture) electronic data capture tools hosted at MD Anderson ²⁷. REDCap (<http://www.project-redcap.org>) is a secure, web-based application with controlled access designed to support data capture for research studies, providing: 1) an intuitive interface for validated data entry; 2) audit trails for tracking data manipulation and export procedures; 3) automated export procedures for seamless downloads to common statistical packages; and 4) procedures for importing data from external sources. In the case of multi-center studies REDCap uses Data Access Groups (DAGs) to ensure that personnel at each institution are blinded to the data from other institutions. REDCap (<https://redcap.mdanderson.org>) is hosted on a secure server by MD Anderson Cancer Center's Department of Research Information Systems & Technology Services. REDCap has undergone a Governance Risk & Compliance Assessment (05/14/14) by MD Anderson's Information Security Office and found to be compliant with HIPAA, Texas Administrative Codes 202-203, University of Texas Policy 165, federal regulations outlined in 21CFR Part 11, and UTMDACC Institutional Policy #ADM0335. Those having access to the data file include the study PI and research team personnel. All protected health information (PHI) will be removed from the data when it is exported from REDCap for analysis. All dates for a given patient will be shifted by a randomly generated number between 0 and 364, thus preserving the distance between dates. Dates for each

patient will be shifted by a different randomly generated number. Following publication study data will be archived in REDCap.

General descriptive statistics will be computed to report toxicity and outcome metrics. In addition, descriptive statistics will describe pretreatment patient demographics including age, gender, and performance status as well as disease-related characteristics including disease tumor and nodal stage. All time to event analyses will start from the time of enrollment.

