7.2 Enrollment

Anticipated enrollment is 1 patient every other month. We should be able to enroll 48 evaluable patients over 8 years. We anticipate 8 patients may not be evaluable such that we will have a total of 40 evaluable patients on this trial. Following enrollment of the last patient, we anticipate 6 months of follow up to obtain adequate toxicity data for the primary endpoint. Thus, we anticipate that this trial will take approximately 6-8 years to complete.

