7.4 Statistical Analysis Plan

7.4.1 Primary Clinical Endpoint: *To assess physician-reported acute grade 3 or greater gastrointestinal, genitourinary and hematologic toxicities at 12 weeks post-treatment for patients treated with linear energy transfer (LET)-optimized, intensity-modulated proton therapy (IMPT) and compare to contemporary controls treated with VMAT to determine the feasibility of this outcome for a future randomized trial.*

- At baseline, weekly during treatment, and at the 12 week post-treatment follow up appointment, the treating physician will document physician-assessed acute hematologic, gastrointestinal, genitourinary, dermatologic and other toxicities according to the Common Toxicity Criteria for Adverse Events v-4 (CTCAE v4).
- For each cumulative physician-reported toxicity (hematologic, gastrointestinal, genitourinary, dermatologic and other) at 12-weeks post-treatment, we will tabulate results by type, grade, and attribution and compare with contemporary controls treated with standard of care VMAT-based chemoradiation with 5FU and cisplatin for non-metastatic anal squamous cell carcinoma manually and individually matched for (in order): T-stage, radiation dose, age and gender. We will compare toxicity rates using a McNemar's chi-squared test for paired proportions.
- A separate PA protocol will be submitted to retrospectively review the data from these contemporary controls.
- Subset analyses will be carried out to evaluate the effect of other variables that may also impact toxicity in addition to radiation modality (IMPT vs VMAT).

On RTOG 0529, patients treated with dose-painted IMRT-based concurrent CRT for anal cancer had reported worst overall G3 or greater toxicity rates of 83%. GU/GI G3 or greater toxicity rates were 21%, dermatologic G3 or greater toxicity rates were 23% and hematologic G3 or greater toxicity rates were 58% ⁴.

To ensure an LET-optimized IMPT-based CRT approach is not overly toxic, we will monitor physician-assessed toxicity using the Bayesian optimal phase 2 (BOP2) design ²⁸. Specifically, let n denote the interim sample size and N denote the maximum sample size. Let p_{tox} denote the probability of G4 or greater toxicity and define the null hypothesis $H_0: p_{tox} > 0.5$, representing that the treatment is too toxic. We will stop enrolling patients and inspect the safety data for possible trial termination if

$$Pr(p_{tox} \leq 0.5 | data) < \lambda \left(\frac{n}{N}\right)^\alpha,$$

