where λ and α are design parameters optimized to minimize the chance of incorrectly claiming that a safe treatment is unacceptable under the alternative hypothesis $H_1: p_{tox} = 0.3$, while controlling the type I error rate at 0.1 (i.e., the chance of incorrectly claiming that an overly toxic treatment is acceptable is no more than 10%). Assuming a Beta (0.5,0.5) prior distribution for p_{tox} , the above decision rule corresponds to the following stopping boundaries:

Table 3: Optimized stopping boundaries

# patients treated	Stop if # toxicity >=
10	7
20	11
30	14
40	16

Based on Table 3, we perform the interim analysis when the number of enrolled patients reaches 10, 20, 30. When the total number of patients reaches the maximum sample size of 40, we reject the null hypothesis and conclude that the treatment is acceptable if the number of toxicities are less than 16; otherwise we conclude that the treatment is unacceptable. We anticipate we will have to enroll 48 patients to have 40 evaluable patients for this analysis.

Below in Table 4 are the operating characteristics for the safety monitoring based on 10000 simulations using the BOP2 web application, which is available at <http://www.trialdesign.org>.

Table 4: Operating characteristics

Toxicity rate	Early stopping (%)	Claim acceptable (%)	Sample size
0.5	72.70	7.31	26.7

0.4	30.55	42.83	34.9
0.3	4.93	87.57	39.1
0.2	0.17	99.57	40.0
0.1	0.00	100.00	40.0

7.4.2 Secondary Clinical Endpoints:

- Secondary Endpoint #1: *To assess the feasibility of enrolling patients on a prospective trial delivering LET-optimized IMPT for newly diagnosed, non-metastatic anal cancer.*
 - We will assess accrual at 24 months after the study open to determine feasibility of enrolling 40 patients and obtaining insurance approval for IMPT treatment over the planned 9 years.
- Secondary Endpoint #2: *To develop guidelines and workflow to create and deliver anal canal cancer treatments using LET-optimized IMPT.*
 - We will present the results of our workflows in a descriptive manner.
- Secondary Endpoint #3: *To evaluate complete response rate at 12 weeks and 24 weeks post-treatment.*
 - Complete response will be defined as no evidence of disease by physical exam, endoscopy and cross-sectional imaging.
 - Complete response will be reported at 12 and 24 weeks post-treatment as determined clinically by physical exam, endoscopic examination and imaging.

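### The matched toxicity comparison is meant to inform a randomized trial, but the plan specifies a McNemar test without a paired difference or confidence interval

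*Combined protocol and SAP*

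**What the plan says.** Section 1.1.1 sets the purpose of the comparison with VMAT controls: "to determine the feasibility of this outcome for a future randomized trial". Section 7.4.1 repeats it.

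For each toxicity category, section 7.4.1 says "we will tabulate results by type, grade, and attribution". Controls are to be "manually and individually matched for (in order): T-stage, radiation dose, age and gender", and rates are compared by a McNemar "chi-squared test for paired proportions". Section 7.1 adds only a general line: "General descriptive statistics will be computed to report toxicity and outcome metrics".

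For the matched comparison, neither section names a difference, ratio, confidence interval, significance level or target effect. Neither says how the result becomes a judgement about a randomized trial. By contrast, Secondary Endpoint #4 in section 7.4.2 promises 95% confidence intervals for LPFS, DMFS and OS.

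On size, section 7.2 expects that "we will have a total of 40 evaluable patients on this trial", and section 7.4.1 agrees: "We anticipate we will have to enroll 48 patients to have 40 evaluable patients for this analysis".

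**The concern.** Planning a randomized trial on this outcome takes three things: the event rate in each group, the size of the difference, and how precisely that difference is known. A test of no difference supplies none of them. A tabulation can supply the rates and, by subtraction, a crude difference, but not its uncertainty. That uncertainty depends on the discordant pairs, which marginal tables do not show.

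The gap matters most when the test is non-significant. Such a result fits both no benefit and a benefit large enough to justify a modest trial. If it is reported without an interval, the team designing that trial cannot tell the two apart.

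**Working it through.** **1. The plan's own figures for N = 40.** The only operating characteristics given are for BOP2 monitoring of grade 4+ toxicity. I recomputed them exactly, with looks at 10, 20, 30 and 40 patients and stopping at 7, 11, 14 and 16 toxicities. The chance of claiming acceptability is 7.38% at a true rate of 0.5 (plan: 7.31%), 42.81% at 0.4 (42.83%) and 87.50% at 0.3 (87.57%). These figures reproduce to within simulation error. They say nothing about the grade 3+ matched comparison, for which no figure is stated.

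**2. Inputs for the matched comparison.**
- Pairs: 40, if matching is one-to-one and every evaluable patient finds a match (assumption).
- Control rates: section 7.4.1 reports for the cited phase II IMRT trial that "hematologic G3 or greater toxicity rates were 58" percent, and a pooled GU/GI rate of 21%. I borrow both as control rates (assumption).
- Two-sided 0.05, no continuity correction, within-pair correlation φ from 0 to 0.4 (assumptions).

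**3. Formulas.** With control rate p1 and IMPT rate p2:
- both members affected: p11 = p1·p2 + φ·√[p1(1−p1)p2(1−p2)]
- discordant probabilities: b = p1 − p11 and c = p2 − p11
- power = sum over m of Bin(m; 40, b+c) × P[(2K−m)²/m exceeds the 5% chi-squared point], with K ~ Bin(m, b/(b+c))
- approximate 95% half-width of the paired difference = 1.96·√[(b + c − (p1−p2)²)/40]

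Example, 58% to 40% with φ = 0: p11 = 0.232, b = 0.348, c = 0.168 and b + c = 0.516. The half-width is 1.96·√[(0.516 − 0.0324)/40] = 0.216. Summing over m gives power 0.367.

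**4. Results** (each range runs from φ = 0 to φ = 0.4).

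| Control to IMPT | Power, uncorrected | Power, continuity-corrected | Half-width (points) |
|---|---|---|---|
| 58% to 48% | 15-19% | 9-13% | 22-17 |
| 58% to 43% | 27-38% | 19-29% | 22-17 |
| 58% to 40% | 37-52% | 27-42% | 22-17 |
| 58% to 38% | 44-62% | 33-51% | 22-17 |
| 58% to 29% (halved) | 76-93% | 66-89% | 21-16 |
| 21% to 10.5% (halved) | 23-36% | 15-21% | 16-12 |
| 21% to 10% | 25-39% | 17-24% | 16-12 |

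**5. What the interval adds.** Take an illustrative table of 40 pairs: both affected 11, VMAT only 12, IMPT only 7, neither 10. The rates are 23/40 = 57.5% and 18/40 = 45%.
- McNemar: (12−7)²/19 = 1.32, p = 0.25. With continuity correction, 16/19 = 0.84, p = 0.36.
- Paired difference: (12−7)/40 = 12.5 points.
- Newcombe paired interval: the Wilson limits are 0.422 to 0.715 and 0.307 to 0.602. The correlation term is (11·10 − 12·7 − 20)/√(23·17·18·22) = 6/393.5 = 0.015. The 95% interval is −8.9 to 32.3 points.

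The test says only that the result is not significant. The interval leaves reductions of 10, 20 and 30 points all open. From a 58% control rate, a two-arm trial (two-sided 0.05, 80% power) would need about 390, 97 and 42 patients per arm respectively.

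**The case against.** The strongest reply is that the plan does more than run a test. It tabulates toxicity by type and grade and promises descriptive statistics. If the controls are tabulated the same way, which is the natural reading, both rates are visible and the crude difference follows. This stands: a reader might infer that the plan produces only a p-value, and the documents do not support that. What is absent is the interval, the discordant-pair counts and a stated use for them.

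A reader might also infer that a null result is likely even if IMPT brings a large benefit. That is too broad, because a halving of hematologic toxicity from 58% would be detected 76-93% of the time.

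A third tempting reading is that the chi-squared version is unreliable in sparse categories such as GU alone. The documents give no separate GU rate. At an assumed 5% rate in both groups, the uncorrected test's size is about 4%, which is not inflated. An exact or mid-p version is a matter of preference.

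Finally, nothing in the plan says that non-significance would mark the outcome as unsuitable, and this is a single-arm feasibility study whose only formal decision rule is the grade 4+ monitoring. That is fair. The difficulty is that the plan gives no other route from the comparison to its stated purpose.

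**Conclusion.** The point holds as a minor one. For an objective about planning a randomized trial, a test is specified where an estimate with its uncertainty is needed. Under the stated assumptions, a non-significant result is more likely than not for hematologic reductions up to about 15 points (power at most 38%) and for a halving of GI/GU toxicity (23-36%). The 95% interval would reach roughly 16-22 points either side for hematologic toxicity and 12-16 for GI/GU reductions of about half.

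These sizes depend on things the documents leave open: the matching ratio and completeness, the significance level, the version of the test and the within-pair correlation. The control rates are also borrowed. They come from a trial of 5FU with mitomycin, whereas the controls here receive 5FU and cisplatin, and the 21% pools GU with GI while the plan analyses them separately. The absence of a planned interval depends on none of this.

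**What to change.** In section 7.4.1, make the primary output for each toxicity category the grade 3+ rate in each group, the counts of discordant pairs in each direction, and the paired risk difference with a 95% confidence interval (for example Newcombe's paired or Tango's score interval). State that these are the planning inputs for the randomized trial. Keep McNemar's test as supportive and say whether the continuity correction is used. State the matching ratio, since these intervals assume one-to-one pairs.

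The cost is SAP wording and a wider results table. The same matched data serve, with no extra patients, visits or assessments.

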6.2 On-treatment Procedures

6.2.1 Radiation treatment will be preceded approximately 1 week or more by radiation treatment planning simulation consisting of a non-contrast CT scan in the treatment position. At least one verification CT scan in the treatment position is required after the initiation of treatment. The treating radiation oncologist should review the internal anatomy on the verification scan with respect to the initial treatment planning scan and review the target coverage as well as doses to normal organs on the verifications scan with respect to the initial treatment plan. Adaptive plans can be generated if deemed clinically necessary by the treating radiation oncologist. Additional verification scans can be obtained up to weekly if deemed necessary by the treating radiation oncologist. See section 5.1 for further details on radiation treatment.

6.2.2 Chemoradiation will be administered using doses of both radiation and chemotherapy consistent with the current institutional standard of care (further details provided in sections 5.1 and 5.2).

6.2.3 On-treatment evaluation consists of weekly clinic visits with the treating radiation oncologist who will assign CTCAE v4 toxicity grades of hematologic, gastrointestinal, genitourinary and dermatologic side effects GI: nausea, vomiting, diarrhea, constipation, anal pain, proctitis, and fecal incontinence; GU: urinary frequency, urinary urgency, urinary tract pain, urinary incontinence, vaginal pain (women only), and perineal pain; Dermatological: radiation dermatitis). Patients will also report toxicity using the PRO-CTCAE. Weekly blood work will be monitored by both the treating medical and radiation oncologists including: complete blood count (CBC: hemoglobin, hematocrit, WBC with differential blood cell counts (neutrophils, bands, lymphocytes, monocytes, eosinophils, basophils, platelets, and febrile neutropenia). A focused physical examination, weight and ECOG performance status will be assessed at each weekly visit.

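### The paired toxicity comparison sets prospective weekly CTCAE grades for IMPT against retrospectively reviewed VMAT data, and nothing requires a common item list, CTCAE version, time window or source

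*Combined protocol and SAP*

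**What the plan says.** The comparison is part of the primary objective. Section 7.4.1 aims to assess acute grade 3 or higher toxicity and "compare to contemporary controls treated with VMAT to determine the feasibility of this outcome for a future randomized trial".

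**IMPT patients.** Section 6.2.3 sets out "weekly clinic visits with the treating radiation oncologist who will assign CTCAE v4 toxicity grades of hematologic, gastrointestinal, genitourinary and dermatologic side effects". The items are named:
- seven GI: "GI: nausea, vomiting, diarrhea, constipation, anal pain, proctitis, and fecal incontinence"
- six GU: "GU: urinary frequency, urinary urgency, urinary tract pain, urinary incontinence, vaginal pain (women only), and perineal pain"

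Section 7.4.1 repeats the schedule: "At baseline, weekly during treatment, and at the 12 week post-treatment follow up appointment, the treating physician will document physician-assessed acute" toxicity under CTCAE v4. Section 6.4.3 sends toxicities to a trial database, and section 7.3 requires at least one weekly CTCAE assessment for evaluability. The trial is single-arm and lists blinding as not applicable (section 1), so the grader knows the modality.

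**VMAT controls.** Section 7.4.1 gives one sentence on data collection: "A separate PA protocol will be submitted to retrospectively review the data from these contemporary controls". It names no item list, CTCAE version, grader, assessment window, evaluability rule or rule for missing grades.

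**Analysis.** Controls are individually matched on T-stage, radiation dose, age and gender. Then: "We will compare toxicity rates using a McNemar's chi-squared test for paired proportions".

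**The concern.** McNemar's test compares two recorded proportions and takes each record at face value. Here every IMPT record comes from one process and every VMAT record from another, so method of ascertainment and modality coincide completely. The matching factors describe the patient and the treatment, not how toxicity was captured. The planned subset analyses cannot separate the two either, because no patient in either group is measured by the other group's method.

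The error could run either way. Prompted weekly grading may find events that a chart review misses, which would make IMPT look worse. A physician who knows the modality, and who chose the plan (section 5.1.2, step 5), may grade leniently, which would make IMPT look better. The result is meant to inform whether this outcome suits a future randomized trial, so an artefact in either direction could mislead that decision.

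The issue is sharpest for GI and GU symptoms. Haematologic grades rest on blood counts and depend less on the grader, though they still depend on how often blood is drawn.

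**Working it through.** **1. The plan's own figures.** The only design calculation is the BOP2 safety rule (Tables 3 and 4). An exact binomial recursion over looks at 10, 20, 30 and 40 patients gives probabilities of claiming acceptable of 7.38, 42.81, 87.50, 99.58 and 100.00% at toxicity rates of 0.5, 0.4, 0.3, 0.2 and 0.1. Table 4 states 7.31, 42.83, 87.57, 99.57 and 100.00%, so it reproduces within simulation error. The rule uses grade 4 or higher toxicity in trial patients only and does not depend on the controls. The plan states no power, alpha or effect size for McNemar's test, so there is no figure to reproduce for this comparison.

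**2. Inputs for the illustration.**
- True grade 3+ GI/GU rate: 21%, the RTOG 0529 figure quoted in section 7.4.1. That trial used mitomycin, whereas the controls receive cisplatin, so this is only a working value.
- Relative capture s: the share of true events recorded in the less completely recorded group. Assumed 0.5 to 0.9; the documents give no value.
- 40 matched pairs (from 40 evaluable patients), two-sided alpha 0.05, zero within-pair correlation and the uncorrected test: all assumed.

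**3. Spurious difference with no true modality effect.** Difference = 0.21 × (1 − s).
- s = 0.9: 0.21 × 0.1 = 2.1 points (21.0% against 18.9%)
- s = 0.7: 0.21 × 0.3 = 6.3 points (21.0% against 14.7%)
- s = 0.5: 0.21 × 0.5 = 10.5 points (21.0% against 10.5%)

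**4. Effect on the test.** With recorded rates a (IMPT) and b (VMAT), the two kinds of discordant pair have probabilities a(1 − b) and b(1 − a). At s = 0.5 for the controls these are 0.21 × 0.895 = 0.188 and 0.105 × 0.79 = 0.083. Enumerating all outcomes for 40 pairs, with events under-recorded in the controls:

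| s (controls) | False 'IMPT worse', no true difference | Shows benefit if IMPT truly halves the rate (10.5% vs 21%) |
|---|---|---|
| 1.0 | 2.2% | 22.4% |
| 0.9 | 3.8% | 16.1% |
| 0.7 | 9.7% | 7.0% |
| 0.5 | 22.4% | 2.3% |

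At s = 0.5 a true halving disappears from the recorded data (10.5% in both groups). With continuity correction the middle column reads 1.2, 2.1, 6.0 and 15.4%.

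**5. The opposite direction.** If IMPT events are under-graded by the same factors and controls are recorded fully, the middle column becomes the chance of a false 'IMPT better' result: 3.8, 9.7 and 22.4% at s = 0.9, 0.7 and 0.5.

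**6. Sensitivity to the base rate.** At s = 0.5 the false-result probability is 12.0% with a base rate of 10% and 34.5% with 30%.

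**The case against.** The strongest reply is the footnote to Table 1, which describes every listed procedure as standard of care. Weekly physician CTCAE grading is one of those rows. If it is also routine for VMAT patients, their charts already hold contemporaneous grades, and the retrospective review only extracts them. This stands as a real possibility. The footnote concerns the trial's own schedule, however, and does not say that control charts contain such grades or use the same items.

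A reader might go further and infer that control toxicity will be reconstructed from free text, or that the comparison is known to be biased against protons. The documents support neither. They say when control data are reviewed, not how they were first recorded, and the separate protocol, which is not part of these documents, may specify this.

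Three further replies have weight.
- VMAT notes were also written by clinicians who knew the modality, so lack of blinding is not unique to IMPT.
- No decision rule rests on McNemar's test. Even with full capture, 40 pairs have only about a 22% chance of detecting a halving of the GI/GU rate, so the comparison stays weakly informative.
- Re-abstracting IMPT charts does not fully equalize the groups, because those notes come from prompted, unblinded visits.

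These limit the severity and what the remedy can achieve. They do not supply the missing requirement for common measurement.

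**Conclusion.** The concern holds as a gap in specification. The plan compares two groups whose toxicity is ascertained differently, or at least is not required to be ascertained alike, and the analysis cannot separate that from modality. Direction and size are unknown. The 2.1 to 10.5 points rest on a 21% base rate from a mitomycin-based trial and an assumed 50-90% relative capture. They show what is possible and do not estimate the bias. The false-result probabilities also assume 40 uncorrelated pairs and alpha 0.05.

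It should be corrected because the comparison is in the primary objective and a better method is cheap. It does not undermine the trial: safety monitoring and the descriptive IMPT results are unaffected.

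**What to change.** Amend section 7.4.1 as follows.

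1. **Haematologic comparison.** In both groups, derive grades by applying CTCAE v4 cut-offs to recorded CBC values over the same windows: weekly on treatment plus the 12-week visit.
2. **GI/GU comparison.** Abstract both groups from routine records with one form, the same CTCAE v4 item list and the same windows, keeping abstractors unaware of modality where existing staff make this feasible. Present this paired comparison beside the prospective IMPT grades.
3. **Completeness.** Report the share of controls with contemporaneous weekly grades. If it is low, interpret the GI/GU comparison as descriptive; what counts as low should be fixed before the groups are compared.
4. **Unchanged.** Keep the prospective grades for BOP2 monitoring and the descriptive IMPT tables.

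The separate control protocol should carry the same form and definitions.

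**Cost.** About 40 extra abstractions with a form that the controls need anyway, plus SAP wording. Abstracted IMPT GI/GU rates will be less complete than the prospective ones, which is why both are shown. Common abstraction reduces the bias without eliminating it.

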7.3 Evaluability

To be evaluable for toxicity, patients must have at least one weekly assessments of adverse events (CTCAEv4).

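### The toxicity looks are triggered by enrolment, but Tables 3 and 4 assume complete outcomes on 10, 20 and 30 patients, so the printed early-stopping rate is not secured by the rule as written

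*Combined protocol and SAP*

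**What the plan says.** All references are to the combined protocol and SAP.

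- **Look trigger (7.4.1):** "we perform the interim analysis when the number of enrolled patients reaches 10, 20, 30".
- **Boundaries (7.4.1, Table 3):** stop at 7 or more toxicities in 10, 11 in 20, 14 in 30 and 16 in 40. The rows are indexed by "patients treated".
- **Final rule (7.4.1):** acceptable if there are fewer than 16 toxicities in 40, followed by "We anticipate we will have to enroll 48 patients to have 40 evaluable patients for this analysis". Section 7.2 agrees: "We anticipate 8 patients may not be evaluable such that we will have a total of 40 evaluable patients on this trial".
- **Evaluability (7.3):** a single weekly toxicity grading is enough.
- **Toxicity recording (7.4.1):** "At baseline, weekly during treatment, and at the 12 week post-treatment follow up appointment, the treating physician will document" toxicities. The primary endpoint uses the cumulative toxicity at 12 weeks after treatment.
- **Waiting time (7.2):** "Following enrollment of the last patient, we anticipate 6 months of follow up to obtain adequate toxicity data for the primary endpoint". No corresponding wait is stated for the interim looks.
- **Consequence of reaching a boundary (7.4.1):** "We will stop enrolling patients and inspect the safety data for possible trial termination if" the posterior probability falls below the threshold λ(n/N)^α. The values of λ and α are not printed.

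**The concern.** One monitoring rule is described in three units: enrolled, treated and evaluable. The plan's own figures show that they differ, because 48 enrolled are expected to yield 40 evaluable. In proportion, 10, 20 and 30 enrolled would hold about 8.3, 16.7 and 25 evaluable patients (multiply by 40/48).

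Timing is a second gap. Table 1 allows screening and consent up to 4 weeks before chemoradiation. A patient whose enrolment triggers a look therefore need not have had any on-treatment grading. Reading *enrolled* as *evaluable* narrows this gap but does not close it, since one weekly grading makes a patient evaluable while most of the toxicity window is still open.

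At stake is the early protection shown in Table 4. If a look has fewer known outcomes than its row assumes and the same count is required, an over-toxic regimen reaches the review trigger less often than printed.

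**Working it through.** **Inputs.** Boundaries 7/10, 11/20, 14/30 and 16/40 (Table 3); Beta(0.5, 0.5) prior, unacceptable rate 0.5, alternative 0.3 (7.4.1); 40 evaluable of 48 enrolled (7.2, 7.4.1); one patient every two months (7.2).

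**Method.** Exact binomial recursion. Carry forward the distribution of the cumulative toxicity count, remove the probability at or above the boundary at each look, and continue with the rest.

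**Step 1. Reproduce Table 4 with complete data on 10/20/30/40.** At rate 0.5 the first look stops with probability P(X ≥ 7 | 10, 0.5) = 176/1024 = 17.19%. The second and third looks add 26.27% and 28.89%, giving 72.34% in total.

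| True rate | Early stop, exact (printed) | Accept, exact (printed) | Expected N, exact (printed) |
|---|---|---|---|
| 0.5 | 72.34% (72.70) | 7.38% (7.31) | 26.7 (26.7) |
| 0.4 | 30.84% (30.55) | 42.81% (42.83) | 34.9 (34.9) |
| 0.3 | 5.03% (4.93) | 87.50% (87.57) | 39.2 (39.1) |

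The agreement is within simulation error, so Table 4 assumes complete outcomes at each look.

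**Step 2. Table 3 counts at the enrolment trigger, newest patient unseen.** Known outcomes are 9/19/29 and the counts stay at 7/11/14. The first look stops with probability P(X ≥ 7 | 9, 0.5) = 46/512 = 8.98%. The later looks add 24.70% and 31.98%, giving 65.67%. At rate 0.4, early stopping falls from 30.8% to 24.9%.

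**Step 3. Newest patient partly seen.** Let a toxicity in the newest patient be visible at that look with probability v, and fully known by the next. At rate 0.5, v = 0.2 gives 67.1%, v = 0.5 gives 69.1% and v = 1 returns 72.3%. The documents give no value for v, so 0.2 and 0.5 are assumptions.

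**Step 4. Enrolled read literally, non-evaluable patients included.** Place 8 non-evaluable patients at random among 48 enrolment positions (assumed), with every evaluable outcome known and looks at 10/20/30 enrolled. Early stopping at 0.5 is about 37%.

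**Step 5. Re-evaluate the posterior rule instead of fixing the counts.** The posterior is Beta(0.5 + y, 0.5 + n − y), and the look stops if Pr(p ≤ 0.5) < λ(n/40)^α. A grid search finds that λ of about 0.898-0.942 with α of about 0.885-1.33 contains the pairs that return Table 3. Over those pairs, at rate 0.5:

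- 9/19/29 known: cut-offs 6-7/10-11/14, early stop 65.7-69.9%.
- 8/18/28 known: cut-offs 6/10/13-14, early stop 62.0-73.0%.

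**Step 6. False acceptance at 0.5.** It is 7.38% as designed and 7.53% with the newest patient unseen. Fewer interim stops can only raise it, up to the value with no interim look at all: P(X ≤ 15 | 40, 0.5) = 7.69%. The 10% limit therefore holds if the final count is complete on 40.

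**Step 7. Expected enrolment at 0.5.**

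- Step 2 reading: 10(0.0898) + 20(0.2470) + 30(0.3198) + 40(0.3433) = 29.2.
- Looks with complete data, two more patients enrolled by each look: 12(0.1719) + 22(0.2627) + 32(0.2889) + 40(0.2766) = 28.1. With three more it is 28.9.

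**The case against.** **The formula, not Table 3, is the rule.** Section 7.4.1 states the rule as a posterior probability given the data and says that Table 3 corresponds to it. Nothing tells the team to hold nine outcomes against the cut-off for ten. This stands in part. A reader might take 65.7% as a maximum, and the documents do not support that: it needs fixed counts and a newest patient who contributes nothing. Steps 3 and 5 give higher values, one of them (73.0%) above the design figure. But without λ and α, no one can recompute a cut-off from the plan as printed.

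**Enrolled is used loosely.** Section 7.2 itself speaks of enrolling 48 evaluable patients, and the text after Table 3 names 40 evaluable patients as the analysis unit. A reader might infer that the plan halves its early protection, to about 37%. That needs the literal reading and an assumed random placement. If *enrolled* means *evaluable*, that figure falls away and only the follow-up gap remains.

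**No data cut is stated.** The plan says when a look is triggered, not that data are locked that day or that unseen patients count as event-free. This is fair; the defect is an unstated requirement, not a stated wrong one.

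**The consequence is modest.** The boundary leads to review for possible termination, and Section 6.4.2 has adverse events assessed throughout. This stands. A reader might also infer that the 10% error limit is breached, or that a removed patient's toxicity is deleted. Step 6 rules out the first as an effect of look timing. On the second, Section 6.4.1 permits substitution but does not say that an observed event is dropped.

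**Conclusion.** The inconsistency is in the text and is certain: three units for one rule, and no follow-up required before a look. Table 4's early-stopping figures hold only for complete outcomes on 10/20/30 patients, which the look rule does not secure.

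The size depends on the reading. With Table 3 counts applied at the enrolment trigger, the loss at a true rate of 0.5 is about 7 percentage points if the newest patient is unseen (72.3% to 65.7%), with the first look falling from 17.2% to 9.0%. It is about 3-5 points if 20-50% of that patient's events are visible. It is larger only if non-evaluable patients count toward the trigger. The final acceptance decision is essentially unaffected, given a complete count on 40. Severity is minor to should-fix.

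**What to change.** In Section 7.4.1:

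1. Replace the enrolment trigger. Each look uses the first 10, 20 or 30 evaluable treated patients, once each has either had a grade 4 or higher event or completed toxicity assessment through the 12-week visit. Use the same unit in Table 3, the look rule and the final rule.
2. State that the review takes place at once if the boundary count is reached earlier among those patients, since later data cannot reverse it.
3. Print λ and α.

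A sentence in 6.4.1 or 7.3 that an observed grade 4 or higher event stays counted after a patient is removed would be a useful but optional clarification.

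**Cost.** Boundaries and maximum sample size do not change, and Table 4's early-stopping and acceptance columns then apply. Formal looks come about 4-5 months later: 5-6 weeks of treatment plus 12 weeks is 17-18 weeks, and up to 22 weeks with the 4-week visit window. At one patient every two months, two or three more patients would be enrolled by then. If accrual stays open, expected sample size at 0.5 rises from 26.7 to about 28-29, which should be stated beside Table 4. These are upper bounds, because item 2 can bring the review forward. Against the rule as written with the newest patient unseen (29.2), the change saves at most about one patient on average. Its main benefit is that the printed early-stopping property becomes true.
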